This is a double-blind, placebo-controlled study. The placebos will be matched to the active supplement in both sensory and physical characteristics. The participants, study investigators, research associates, and study coordinators will have no knowledge of study assignment. Data analysis will be performed blinded to treatment status. The OHSU Research Pharmacy will be responsible for establishing a randomization scheme for newly enrolled participants. Additionally, the Research Pharmacy will ensure blinding of all study medications. We will also evaluate the effectiveness of our blinding by giving study evaluators, participants, study partners, and investigators a short questionnaire asking about knowledge of group assignment. The randomization code will be broken only after data analysis or if there are numerous serious adverse events before the end of the study.

E.6. Compliance

Compliance will be measured informally by a phone check week 6 (i.e., asking how participant is doing taking the supplement). If the participant is not taking the supplement in the appropriate dosage or stopped taking the capsules for longer than 24 hours, the coordinator will speak with the participant about finding ways to increase compliance. Official compliance will be measured in-clinic at Visit 4 via packet count. A participant will be considered compliant if they are \geq 80%.

E.7. Description of Assessments and Procedures E.7.1. Cognitive, Functional, Behavioral Assessments

Neuropsychiatric Inventory Questionnaire (NPI-Q)

The NPI-Q [46] is a structured interview with a caregiver or qualified study partner (defined as having direct contact > 2 days/week) that evaluates both presence and severity of 12 neuropsychiatric features which include: delusions, hallucinations, dysphoria, anxiety, agitation/aggression, euphoria, disinhibition, irritability, lability, apathy, aberrant motor behavior, night-time behavior, and appetite/ eating changes [47]. If the response to the domain question is "No", the informant goes to the next question. If "Yes", the informant then rates both the Severity of the symptoms present within the last month on a 3-point scale ranging from 1 to 3 (mild to severe). Change in overall NPI-Q score between baseline and at 12 weeks will be the primary outcome measure. A modification of the original NPI is the addition of a Caregiver Distress Scale for evaluating the psychological impact of neuropsychiatric symptoms reported to be present. For each feature the caregiver distress score ranges from 1-5 (No distress to extreme distress). The caregiver distress subscale score is the sum of the distress scores for each of the 12 features. Change in overall NPI-Q subscale of caregiver distress score which is the between baseline and at 12 weeks will be a secondary outcome measure.

Clinical Dementia Rating (CDR)

The CDR [48] measures dementia severity and is a global rating of dementia with scores ranging from 0 to 3 (0, 0.5, 1, 2, and 3) rated by a semi-structured participant and informant interview [49]. A trained rater synthesizes information of cognitive performance and functional abilities based on 6 domains which include memory, orientation, judgment and problem solving, community affairs, home and hobbies, and personal care. The scale has good inter-rater agreement [49].

Montreal Cognitive Assessment (MoCA)

A rapid screening instrument for assessing different cognitive domains [50]. Subjects are asked to do the following tasks: 1.) Join 10 randomly displayed numbers and letters in an alternating and sequential fashion. 2.) To measure visuoconstructional skills, accurately copy two drawings, a cube and a clock. 3.) Provide the names of three animals represented by drawings. 4.) Remember a list of 5 words. This is repeated 2 times. After a delay, subjects again recall as many words as possible. 5.) To measure

attention: repeat a five number sequence forward, and a separate three number sequence backwards, signal when a certain letter is read in a spoken sequence of varying letters, and count backwards from 100 by subtracting seven. 6.) Name as many words that start with the letter "F" in sixty seconds. 7.) Explain what pairs of words have in common, such as "Tell me how an orange and a banana are alike." 8.) To provide orientation, provide date, place, and city.

Mini Mental State Examination (MMSE)

The MMSE is among the most widely used screening instruments for cognitive impairment indicative of dementia [51]. This 30 point scale is helpful for comparing across diverse studies, as it has become a common way of communicating severity of dementia among clinicians. Participants must have MMSE score \leq 25 to meet inclusion criteria, indicating a mild to moderate dementia severity. SF-12

The 12-Item Short Form Health Survey (SF-12) is a 12-item validated shortened version of the SF-36 and was designed to provide a health-related quality of life (HRQL) measure that was quick and easy to administer in large population studies. The SF-12 contains a subset of the 12 items from the SF-36 and information from this subset of questions is used to construct a physical and mental component summary score (PCS and MCS, respectively). [52, 53]

Zarit Burden Interview (ZBI) screening version

The Zarit Burden Interview (ZBI) Screening Version is a popular caregiver self-report measure used by many aging agencies, and originated as a 29-item questionnaire. The revised screening version contains 4 items and has been validated. Each item on the interview is a statement, which the caregiver is asked to endorse using a 4-point scale. Response options range from 0 (Never) to 4 (Nearly Always). Change in overall ZBI score between baseline and at 12 weeks will be a secondary outcome measure.

Dietary Screener Questionnaire (DSQ)

The DSQ is a short 26 item questionnaire which asks about the frequency of consumption in the past month of selected foods and drinks. It captures intakes of fruits and vegetables, dairy/calcium, added sugars, whole grains/fiber, red meat, and processed meat. The DSQ can be administered by an interviewer, self-administered, or via the web. [56]

E.7.2. Other Evaluations Serum Lipid Levels

Increased serum lipids levels (cholesterol, LDL) have been implicated as a risk factor for AD [57, 58]. Cholesterol in particular has been implicated in amyloid beta formation [58]. Serum cholesterol, triglyceride, LDL, and HDL will be measured in the Lipid laboratory at OHSU. Associations between serum lipid levels and clinical outcomes will be evaluated. Participants will be asked to fast the night before (10 hours). Measures will be taken at baseline and at 12 weeks.

Apolipoprotein E (Apo E)

Apo E genotype epsilon 4 allele will be collected due to its varied role in Alzheimer's disease and dementia [59]. The relationship between Apo E and the active ingredients of Feru-guard (ferulic acid and Angelica archangelica) remain unexamined and is worthy of investigation. Apo E genotyping will be performed in the Lipid laboratory at OCTRI using the protocol of Hixson and Vernier [60]. Blood draw for Apo E genotyping will occur only at Visit 2 (Baseline).

Safety labs

We will include a comprehensive metabolic panel (BUN, creatinine, sodium, potassium, bicarbonate, chloride, calcium, phosphorus, total bilirubin, direct bilirubin, alkaline phosphatase, SGOT, SGPT, GGT, LDH CPK, total protein, albumin, globulin, and glucose), complete blood count and prothrombin time (PT/INR). All three laboratory measures will be assessed at baseline, and 12 weeks.

Physical Exam

A complete physical exam will be performed by a medically qualified professional at screening and 12 week visits. A review of all major body systems will be performed. Vital signs (height, weight, blood pressure, pulse, temperature, and respiration) will also be performed at these visits.

Neurological Exam

A neurological exam will be performed by a medically qualified professional and will include assessment of cranial nerves, strength coordination, reflexes, sensation, and gait at screening and 12 week visits.

F. DATA AND SPECIMENS:

F.1. Handling of Data and specimens

Upon enrollment, each participant will be assigned a unique identification number by a study coordinator. This number will be used on all of the data collected for that participant, with no personal identifiers on the same source of data. All physical data including questionnaires, exam sheets, and lab reports will be placed in in a participant specific binder and stored in a locked room only accessible to study staff at OHSU in the Hatfield Research Center. The binder with all physical data will be stored in the locked room under the supervision of study staff until it is sent to the Iron Mountain storage facility for archiving once the study is completed.

F.2. Sharing of results with Participants

Research test results will only be shared with the participant, study partner, or the participant's primary care provider if the information is important to their health care. The determination of when to disclose incidental findings will be made by the investigators, or determined necessary by the DSMB. The lab where blood samples will be sent for analysis is CLIA certified.

F.3. Data and Specimen Banking

Data collected through questionnaires, lipid analysis, Apo E, and safety labs (CBC,

PT/INR, and CMP) will be stored to be used only for future analysis by Glovia, Co. Ltd., or the study PIs, [name] and [name].

G. DATA ANALYSIS:

G.1. Statistical Analysis

Aim 1: Determine if Feru-guard can improve BPSD in people with dementia.

This aim tests the hypothesis that Feru-guard supplementation over 12-weeks will improve common behavioral symptoms as measured by NPI-Q in people with dementia. Statistical analyses will be performed by OHSU.

Aim 2: Measure the effect Feru-guard supplementation has on caregiver burden and quality of life, and global cognition in participants.

This aim is exploratory and will be used to collect data on the study drug's effect on caregiver burden (NPI-Q subscale of caregiver distress), quality of life (SF-12 for caregiver) and Zarit Burden Interview (ZBI) screening version over 12 weeks. We will also collect data on changes in global cognition of participants over 12 weeks using the Montreal Cognitive Assessment (MoCA). Statistical analysis will be performed by OHSU.

G.2. Analytic approach

To compare the primary aim of total NPI-Q measure between the Feru-guard and placebo, we will use the mixed model approach to longitudinal data. This method allows for correlation between repeated observations on each participant and provides valid inference in the presence of missing data as long as the data is missing at random (MAR). Sensitivity analysis will be conducted, if warranted, to examine the impact of various assumptions regarding the reasons that parts of the data are missing. Our focus will be on the comparison of the 12 week changes from baseline to assess whether there is greater overall improvement in Feru-guard group compared to placebo. Descriptive information regarding the 12 week change for both groups and the differences in change between the groups will be obtained along with 95% confidence intervals. We will also examine the full profiles over the 12 week time period. In doing so, we will determine whether polynomial models, as opposed to unstructured models, provide a reasonable fit to the data. Given evidence of interaction between time and treatment--i.e. that the changes over time are different between the treatment groups-we will then use our fitted models to make follow-up comparisons between groups at individual time-points. In constructing our models, we will adjust for potential confounders such as dementia type, Apo E4 genotype, gender, and age. Subsequent analyses will incorporate compliance information. The same analysis will be used for outcomes in Aim 2, MoCA, SF-12, and caregiver burden (NPI).

G.3. Sample size estimation

The sample-size calculation was based on a previous open-label study published by Kimura et al. [9]. Since this study is an open-label study, estimated mean difference assumes that the placebo group will not have a change over 12-weeks and we are predicting that treatment will have a lowered NPI score, this effect size provides a reasonable estimate for contrasts between groups for the current study. For individual

contrasts between Feru-guard and placebo we will have a power with sample sizes of n = 32 in each group, and total n = 70 participants to detect a 7 point difference between placebo and Feru-guard, this sample size accounts for 10% participant drop out over 12-weeks.

Table 6. Sample sizes needed to detect differences in change in behavioral symptoms measured by NPI
(total score) between groups with 80 % power using a significance level of 0.05.

(total score) between groups with 80 % power using a significance level of 0.05.								
Group	Estimated mean	Estimated	Sample size needed					
comparisons	differences on NPI total score	standard deviation of change from baseline	for each group to detect a difference with 80% power and 0.05 significance					
Placebo vs. Feru- guard	10.0	9.7	15					
Placebo vs Feru- guard	7.0	9.7	31					
Placebo vs Feru- guard	6.0	9.7	42					

G.4. Randomization

Participants will be randomly assigned to study drug or placebo according to a randomization scheme developed by the Research Pharmacy at OHSU. The study participants, study investigators, research associates, and study coordinators will have no knowledge of study assignment.

G.5. Quality Control

The principal investigator will oversee the management of the participants, intervention, and analysis, which will be carried out by the clinical investigators, research statistician, and research assistant. Data entry, quality control and preparation, and participant management will be ongoing throughout the study.

The quality of data collection will be ensured by having all study staff up-to date on all data collection procedures, with a process of cross checking accuracy of data before and after entry into an online database. Quality of the study supplement will be checked and ensured by the Research Pharmacy at OHSU.

H. PRIVACY, CONFIDENTIALITY, AND DATA SECURITY:

H.1. Privacy and Confidentiality

All research records linked with personal information will be coded with a unique identification number; therefore will contain no personal identifiers. All records with identifying information and linked with identifying information will be physically locked or password protected so that only authorized study staff will have access to them.

H.2. Data Security

All physical data collected about participants will be locked so that only authorized study staff will have access. Data will be kept in locked cabinets separate from identifiers. Computer files will be password protected. No one other than the researchers will have access to identifiable data. All research staff with access to data will have gone through a background check and completed all relevant trainings on data safety and HIPAA compliance through OHSU.

I. MONITORING PLAN:

I.1. DSMB

The study will be monitored by the Data Safety and Monitoring Board (DSMB) of the Oregon Center of Complementary and Alternative Medicine in Neurological Disorders (ORCCAMIND) once a year to ensure participant safety. If a participant reports serious side effects related to the study medication and information on group assignment is believed to be necessary for the participant's safety and well-being, the blind will be broken for that participant. The randomization code will otherwise be broken only after data analysis or if there are numerous reports of serious adverse events before the end of the study. The DSMB has been and will continue to be compliant with NIH Policy for Data and Safety Monitoring.

I.2. Adverse Events

Adverse events (AEs) will be monitored at visits 2-4 as a part of the clinic visits and by phone. Although assessment of adverse events will also include solicitation of non-specific change (e.g., "Do you feel different since beginning the treatment?"), a 12 item adverse events checklist covering all major organ systems will be included to probe for adverse events. The nature of each AE, its severity (mild, moderate, or severe), its likely relationship to study treatment (definite, probable, possible, not related, or unknown), its duration and any necessary treatment modifications or adjustments will be recorded. In addition to recording of AEs, labs to assess basic metabolic function (including liver function tests), plasma lipid levels, a complete blood count, and prothrombin time (PT/INR) will be performed at visit 2 and 4. Participants will be reminded and encouraged during clinic visits and phone checks to contact the study coordinator or a study investigator as soon as a moderate or serious adverse event should occur.

J. RISKS AND BENEFITS

J.1. Potential Risks

Venipuncture: The risks are minimal and may include some pain, bleeding and transient hematomas.

Questionnaires: The risk from filling out questionnaires is minimal; there may be mild anxiety from filling out questionnaires.

Feru-guard: At a daily dose of 360.64 mg ferulic acid and 40.02mg Angelica archangelica per day, the risks are minimal. In previous studies, skin rash and gastrointestinal side effects (constipation, diarrhea) are included as potential side effects. Due to unknown interactions with pharmaceutical medications, we will exclude participants on blood thinning medications (e.g. warfarin) to mitigate risk.

Placebo: The placebo consists of maltodextrin, which is a common starch-based food additive. Possible side effects include allergic reactions, unexplained weight gain, bloating, and flatulence.

J.2. Study Limitations

We are not excluding over-the-counter medications (e.g. NSAIDS) and supplements (e.g. ginkgo, vitamin E). Excluding these types of OTCs may severely hinder recruitment. We will collect information on all prescription, OTC, and nutritional supplementation in participants, which will enable us to analyze association of medication use and outcomes. Our power analysis is limited to data from a published open-label study so estimates needed to be made on the placebo group. This study is a pilot with the intent of using the data collected to more definitively power a larger clinical trial.

J.3. Potential Benefits

Ferulic acid is a potent antioxidant which combats the oxidative stress/toxicity present in a wide range of chronic diseases such as diabetes, cancer, cardiovascular disease, aging of skin, arthritis, neurodegenerative diseases, and chronic inflammation. Though beyond the scope of the current study, it is possible the antioxidant properties of ferulic acid may benefit a participant that has a chronic disease with an oxidative stress/toxicity component, during their 12 weeks on the study supplement.

J.4. Importance of Knowledge to be gained

This study will test if the combination of ferulic acid and Angelica archangelica can improve or prevent further decline in the behavioral and psychological symptoms of demented older people. Currently, treatments designed to improve BPSD center around anti-psychotic medication, with recent growing interest in non-pharmacological therapies. It is an important public health issue to scientifically evaluate the potential benefits of a non-pharmacological therapy for BPSD.

K. CITATIONS

- Oliveira, A. M. D., Radanovic, M., Mello, P. C. H. D., Buchain, P. C., Vizzotto, A. D. B., Celestino, D. L., ... & Forlenza, O. V. (2015). Nonpharmacological interventions to reduce behavioral and psychological symptoms of dementia: a systematic review. BioMed research international, 2015.

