A total of 70 participants 55 years and older will be enrolled, this accounts for a 10% drop out rate. To achieve an enrollment of 70 participants, accounting for a 25% screen fail rate, we anticipate needing to screen 95 participants. Due to the study population being demented, each participant must have a committed caregiver who is able to act as their study partner. The study partner will be asked to accompany the participant to each onsite visit and complete some questionnaires pertaining to the participant's health.

D.2.2. Inclusion and Exclusion Criteria Inclusion

- 55 years old or older.
- Diagnosis of AD, vascular, and mixed dementia
- Neuropsychiatric Inventory Questionnaire (NPI-Q) at least 3 items out of 12 items are rated as "present."
- Use of cholinesterase inhibitors, antidepressants and or antipsychotics medications is allowed, if on stable dosage for at least 2 months.
- Use of memantine and/or serotonin reuptake inhibitors is also allowed, if on stable dose for at least 2 months.
- Have a committed caregiver who is able and willing to assist them with medications, provide study participant information, and attend all study visits.

- Sufficient English language skills to complete all testing.
- MMSE score of 25 or lower.

Exclusion

- MMSE > 25
- Participants who started using antipsychotics or anticholinergics within the previous 2 months.
- Participants on blood thinners such as warfarin (Coumadin, jantoven), rivaroxaban (xarelto), fondaparinux (arixtra), dibigatran (pradaxa), apixaban (eliquis) dalteparin (fragmin), enoxaparin (lovenox). Aspirin use is allowed.
- Participants without an identified caregiver.
- Participants with delirium caused by medicinal poisoning or drug intoxication.
- Participants who have had the following diseases before the onset of cognitive impairment:
 - 1. Alcoholism
 - 2. Manic depression or bipolar disorder
 - 3. Schizophrenia
- Participants with malignancy or an acute inflammatory disease.
- Participants with critical circulatory, respiratory, kidney, or liver disease or diabetes.
- BMI of >30.
- Participants who have taken Feru-guard, ferulic acid, or Angelica archangelica supplementation within the last year.
- Enrollment in another clinical trial or treatment study within the previous 6 months.

D.2.3. Screen failure

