The visit takes place at OHSU, OCTRI. Participants will attend this visit with their study partner (LAR), and they will bring any medications that they are currently taking. The visit will start with a trained research coordinator going over the consent form and participant rights with participant and their study partner, and answer any questions they have. After going through the consent form, the participant, study partner (who is also the LAR), and the study clinician will go through the ACE to determine the capacity to give consent. If the participant is determined to be unable to give consent, then the LAR will give consent form if they agree to participate in the study. The study partner's signature is necessary because he/she will be answering questions as part of the study procedures.

Demographic information and general medical history, including mental health history, family history and history of allergies will be obtained. Participants will have a general physical and neurological exam, including vital measures (for example, weight and blood pressure).

To determine eligibility for participation, the Neuropsychiatric Inventory Questionnaires (NPI-Q) will be administered, with at least 3 items out of 12 being rated as "present" for inclusion. The NPI-Q is also the primary outcome measure and this will serve as a baseline measure of the participant's BSPD. Additionally, the Mini Mental State Exam (MMSE) will be administered to determine eligibility, with inclusion score of 25 or below. The MMSE will only be used to screen in potential participants.

Randomization will occur after this visit by OHSU Research Pharmacy. The participant will be scheduled for Visit 2 within 14 days.

Baseline (Visit 2): This visit will last approximately 1.5 hour.

This visit will be scheduled within 14 days of the screening visit at OHSU and take place at OHSU, OCTRI. Participants that have met all study inclusion/exclusion criteria will be assigned a study number. Since this visit will be performed close to the screening visit, medical history, NPI-Q, and the physical and neurological examination from the screening visit will be used as "baseline" outcomes and will not be repeated at this visit.

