A fasting blood draw will be performed for safety labs and will include: complete blood count, comprehensive metabolic panel, fasting lipid levels (cholesterol, triglycerides, HDL, LDL), prothrombin time (PT/INR), and for Apo E genotyping. About two tablespoons of blood will be collected. Food/light meal will be provided following the fasting blood draw and after all fasted blood draws throughout the study. In order to establish baseline measures of cognitive function, the Clinical Dementia Rating (CDR) and Montreal Cognitive Assessment (MoCA) will be administered. SF-12 will be filled out by the study partner to establish baseline for general sense of health and ability to perform daily tasks. Because cereals are a source of ferulic acid, we will administer the Dietary Screener Questionnaire (DSQ) to establish a baseline for cereals in the participant's diet. In order to provide an additional measure of caregiver burden, the Zarit Burden Interview (ZBI) screening version will be administered.

Any recent changes in medications (prescribed, over-the-counter medications, nutritional supplements, herbals) and any recent changes in diet will be recorded at this visit. Adverse events will be collected at baseline for comparison throughout the study. The study coordinator will dispense a 12-week supply of medication and give both verbal and written instructions on medication dosing.

Week 6 (Visit 3 - Phone): This visit will last approximately 0.5 hour.

This visit will take place over the phone, six weeks after the baseline visit. The study coordinator will record adverse events and any recent changes in medications (prescribed, over-the-counter medications, nutritional supplements, herbals) and any recent changes in diet. Study supplement compliance will be assessed for by asking the participant how many capsules they take a day and have they stopped taking the capsules for longer than 24 hours. If possible, the coordinator will schedule the week 12 visit with the participant.

Week 12 (Visit 4): This visit will last approximately 2.5 hours

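### The NPI-Q that admits a participant is also the primary baseline and is not repeated before dosing, so within-arm 12-week changes include some regression to the mean and up to 14 untreated days; the between-arm comparison is not biased

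*Combined protocol and SAP*

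**What the plan says.** Section E.2, Screening Visit (Visit 1), gives the NPI-Q as an entry test, "with at least 3 items out of 12 being rated as 'present' for inclusion", and continues: "The NPI-Q is also the primary outcome measure and this will serve as a baseline measure". D.2.2 has the same three-item rule.

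For Visit 2, E.2 says "This visit will be scheduled within 14 days of the screening visit". Because the visits are close together, the Visit 1 history, examination and NPI-Q "will be used as 'baseline' outcomes and will not be repeated at this visit". Table 4 agrees and shows the NPI-Q at Visits 1 and 4 only. Dosing starts from Visit 2: "The study coordinator will dispense a 12-week supply of medication". MoCA, SF-12 and ZBI have their baseline at Visit 2.

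On timing, E.2 says of Visit 3 "This visit will take place over the phone, six weeks after the baseline visit", and Visit 4 follows six weeks after that. E.2 also places randomisation after Visit 1, that is, before Visit 2.

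G.2 focuses on comparing 12-week changes between arms. It will also describe the change in each arm, and the difference, with 95% confidence intervals. Its examples of adjustment variables are dementia type, Apo E4 genotype, gender and age; baseline NPI-Q is not among them. G.3 says the "estimated mean difference assumes that the placebo group will not have a change over 12-weeks".

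**The concern.** Participants are admitted because the NPI-Q is high enough on one occasion, and that same reading becomes the starting point for change. Any part of the score that is rating error or a passing fluctuation will tend to fall by the next reading, whatever the capsules contain. Some improvement in the placebo arm is therefore expected, while G.3 plans on none. The documents do not mention regression to the mean.

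The interval is also mislabelled. It runs from Visit 1 rather than from dispensing, so up to two weeks of it are untreated.

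What is at stake is how the within-arm results are read. The aims and J.2 describe this as a pilot whose data will help design and power a larger trial, and J.2 concedes that placebo behaviour had to be guessed. The placebo-arm change is one of the more useful things the pilot can supply, and here it carries a selection effect. In Aim 2, the caregiver distress score, being part of the NPI-Q, starts from a different visit than ZBI and SF-12.

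**Working it through.** **1. The plan's own figure.** Table 6 uses an SD of change of 9.7, 80% power and significance level 0.05. With n per arm = 2 × (1.960 + 0.842)² × 9.7² / d², d = 10, 7 and 6 give 14.8, 30.1 and 41.0, rounded up to 15, 31 and 42. The table reproduces as two-sided. Repeating the NPI-Q does not alter it at a fixed 7-point difference.

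**2. Interval.** Visit 2 to Visit 4 is 6 + 6 = 12 weeks, or 84 days. Adding 0 to 14 days from Visit 1 gives 84 to 98 days. At most 14/98 = 14% of the interval precedes dosing.

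**3. Regression to the mean.** Expected fall in SD units = (1 − correlation) × L, where L = φ(c)/q for a normal score cut so that a proportion q passes.

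- Pass rate: D.2.1 plans a 25% screen-failure rate for all causes, so on the plan's figure at least 75% pass the NPI-Q rule. I take 75-90%. L is 0.424 at 75% and 0.195 at 90%.
- Correlations (assumed; the documents give none): r = 0.7-0.8 from Visit 1 to Visit 2, and r1 = 0.4-0.6 from either pre-dose reading to week 12.

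| Pass rate | Visit 1 to Visit 2, (1 − r)L | Visit 1 to week 12, (1 − r1)L |
|---|---|---|
| 90% | 0.04-0.06 SD | 0.08-0.12 SD |
| 75% | 0.08-0.13 SD | 0.17-0.25 SD |

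A Visit 2 baseline removes the share (1 − r)/(1 − r1). The extremes are 0.2/0.6 = 33% and 0.3/0.4 = 75%.

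**4. Effect on the comparison.** A simulation with no treatment effect used 32 per arm, a 25% cut, a baseline-to-follow-up correlation of 0.7 and the source study's baseline SD of 9.6 (C.2). Mean placebo change was −1.2 points, mean difference between arms 0.0 and type I error 5.0%. A one-sample test of the placebo change at the 5% level rejected in 15% of runs. The effect is on within-arm changes, not on the contrast.

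**5. Precision.** Residual variances, with the SD set to 1 at every reading:

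- Unadjusted change from Visit 1: 2(1 − r1), which is 1.20 at r1 = 0.4 and 0.80 at r1 = 0.6.
- Week-12 score adjusted for Visit 1: 1 − r1², which is 0.84 and 0.64.
- Week-12 score adjusted for the mean of Visits 1 and 2: 1 − 2r1²/(1 + r), which is 0.812-0.822 and 0.576-0.600.
- Change from Visit 2 adjusted for the mean of Visits 1 and 2: 2(1 − r1) − (r1 − m)²/m with m = (1 + r)/2, which is 0.922-0.962 and 0.700-0.726.

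The third is 25-32% below the first (0.600/0.80 = 0.75; 0.812/1.20 = 0.68) and 2-10% below the second (0.822/0.84 = 0.98; 0.576/0.64 = 0.90). The fourth is 9-15% above the second.

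Selection narrows the Visit 1 spread, so the gain over unadjusted change would be smaller if the assumed correlations describe unselected patients. The 2-10% does not depend on this.

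**The case against.** The reuse is deliberate and E.2 gives a reason: the visits are close. That limits the untreated gap but does not undo selection on the same reading. G.2's main interest is the between-arm contrast, which is unaffected, and it presents the within-arm changes as descriptive. Both points stand and keep this modest.

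The rule counts items present, whereas the outcome also scores severity, so the truncation formula probably overstates the effect. The NPI-Q asks about the last month, so a second reading within 14 days covers at least about half the same window and is not independent. Visit 2 comes after randomisation. These points stand too; the last is a real drawback of the fix.

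Three stronger readings are tempting but not supported:

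- **That the primary result is biased.** Baseline precedes randomisation and both arms share the selection and the gap.
- **That the trial is underpowered.** If 7 points were the gross active change, placebo improvement of 1 or 2 points would leave 6 or 5 points, and power at 32 per arm would fall from 82% to 70% or 54%. But Table 6 treats 7 as the difference between arms, and the open-label source fell by 28.3 − 17.7 = 10.6 points. The 3.6-point margin could absorb placebo improvement, though G.3 does not say that it is meant to.
- **That sites or informants inflate scores to gain entry.** Nothing in the documents says the informant knows the threshold.

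Nor does J.2 say that within-arm changes are what will power the next trial; it refers only to the data collected.

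**Conclusion.** The point holds as a limited, worthwhile improvement. The within-arm changes labelled as 12-week span 12 to 14 weeks and include regression to the mean, which is at odds with G.3's assumption of no placebo change. The between-arm comparison is valid as designed.

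At a 75-90% NPI-Q pass rate, about 0.04-0.13 SD of regression arises between Visits 1 and 2. A Visit 2 reading would remove roughly a third to three quarters of the total to week 12. These sizes rest on assumed correlations (r 0.7-0.8, r1 0.4-0.6), a normal approximation, and treating the entry rule as a cut on the total score. I leave them in SD units because the SDs in C.2 are for the ten-symptom NPI, not the NPI-Q.

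The 25-32% precision gain is measured against a plain difference in change. Most of it comes from adjusting for baseline at all; the second reading adds 2-10%. G.2's list is introduced as examples, so a baseline NPI-Q covariate is not ruled out, but none is specified.

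**What to change.** - **E.2 and Table 4:** keep the Visit 1 NPI-Q for eligibility. Repeat the NPI-Q, with caregiver distress, at Visit 2 before capsules are dispensed. Eligibility stays fixed at Visit 1, so a participant with fewer than three items at Visit 2 remains in the trial.
- **G.2, descriptive results:** report within-arm 12-week changes from Visit 2. The interval is then a true 12 weeks, and caregiver distress shares its baseline visit with ZBI and SF-12.
- **G.2, primary comparison:** model the week-12 NPI-Q score with the mean of the Visit 1 and Visit 2 scores as covariate, using Visit 1 alone if Visit 2 is missing. Do not analyse change from Visit 2 with that mean as covariate, since this loses precision.
- **G.3:** replace the assumption of no placebo change with a statement that the 7-point difference is net of any placebo improvement.

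The cost is one short informant questionnaire at a visit the study partner already attends, one cell in Table 4 and a few sentences. Visit 2 becomes slightly longer. The second reading falls after randomisation and will be missing for anyone who does not attend Visit 2; it is still blinded and pre-dose, so treatment cannot have affected it.
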